11.3 Management of Pneumonitis in patients receiving Buparlisib

All patients participating in clinical trials with buparlisib will be routinely asked about and observed for the occurrence of adverse events which could include new or changed pulmonary symptoms (consistent with lung abnormalities). Additionally, chest X-rays will be performed every other cycle to further assess the development of pneumonitis. CT scans and pulmonary function tests should be done, as clinically indicated, or if there are symptoms that indicate that the patient has developed pneumonitis. In case of a documented pneumonitis, the guidelines (including dose modifications) in Table 12 should be followed. Consultation with a pulmonologist is highly recommended for any pneumonitis case during the study treatment.

Table 12 Management of Pneumonitis

Worst Grade Pneumonitis	Required Investigations	Management of Pneumonitis	Buparlisib Dose Adjustment
Grade 1	CT scans with lung windows. Repeat at least every 8 weeks, (or as per local practice) until return to within normal limits.	No specific therapy is required	Administer 100% of Buparlisib dose.

Worst Grade Pneumonitis	Required Investigations	Management of Pneumonitis	Buparlisib Dose Adjustment
Grade 2	CT scan with lung windows. Consider pulmonary function testing includes: spirometry, DLCO, and room air O ₂ saturation at rest. Repeat at least every 8 weeks, (or as per local practice) until return to within normal limits. Consider a bronchoscopy with biopsy and / or BAL.	Symptomatic only. Consider corticosteroids if symptoms are troublesome.	Reduce buparlisib dose by 1 dose level (see Table 5) until recovery to ≤ Grade 1. Study treatment may also be interrupted if symptoms are troublesome. Patients will discontinue study treatment if they fail to recover to ≤ Grade 1 within 28 days.
Grade 3	CT scan with lung windows and pulmonary function testing includes: spirometry, DLCO, and room air O ₂ saturation at rest. Repeat at least every 6 weeks, (or as per local practice) until return to within normal limits. Bronchoscopy with biopsy and / or BAL is recommended.	Consider corticosteroids if infective origin is ruled out. Taper as medically indicated.	Hold treatment with buparlisib until recovery to ≤ Grade 1. May restart study treatment within 28 days at a reduced dose (by one level) if evidence of clinical benefit.
Grade 4	CT scan with lung windows and required pulmonary function testing, if possible, includes: spirometry, DLCO, and room air O ₂ saturation at rest. Repeat at least every 6 weeks, (or as per local practice) until return to within normal limits. Bronchoscopy with biopsy and / or BAL is recommended if possible.	Consider corticosteroids if infective origin is ruled out. Taper as medically indicated.	Discontinue treatment with buparlisib.

11.4 Guidelines for the treatment of buparlisib induced hyperglycemia

Buparlisib may affect glucose homeostasis which could result in increases of plasma glucose and insulin levels. Optimal glucose control should be achieved before starting a patient on study treatment and patients requiring insulin should be treated with caution. Patients with hyperglycemia should be instructed to follow dietary guidelines provided by the American Diabetes Association. They may also need to initiate, continue or intensify medication with appropriate anti-diabetic treatment including insulin or oral agents. (Note: some oral antidiabetic drugs are CYP2C9 substrate and should be used with caution; others are CYP3A inducers or inhibitors and are prohibited; See Appendix 1 and Appendix 2, respectively, for more details). Patients who develop Grade 3 or 4 hyperglycemia should be managed urgently as per standard clinical practice, with the goal of stabilizing glycemic control within 24 hours.

11.5 Guidelines for the treatment of study drug induced stomatitis/oral mucositis

General guidance and management include patient awareness and early intervention.

Evaluation for herpes virus or fungal infection should be considered.

Patients should be informed about the possibility of developing mouth ulcers/ oral mucositis and instructed to report promptly any signs or symptoms to their physician, Patients should be educated about good oral hygiene, instructed to avoid spicy/acidic/salty foods, and should follow the following guidelines:

- For mild toxicity (grade 1), use conservative measures such as non-alcoholic mouth wash or salt water (0.9%) mouth wash several times a day until resolution.
- For more severe toxicity (grade 2 in which case patients have pain but are able to maintain adequate oral alimentation, or grade 3 in which case patients

cannot maintain adequate oral alimentation), the suggested treatments are topical analgesic mouth treatments (i.e., local anesthetics such as benzocaine, butyl aminobenzoate, tetracaine hydrochloride, menthol, or phenol) with or without topical corticosteroids, such as triamcinolone oral paste 0.1% (Kenalog in Orabase[®]), or as per local practice.

- Agents containing alcohol, hydrogen peroxide, iodine, and thyme derivatives may tend to worsen mouth ulcers. It is preferable to avoid these agents.

Antifungal agents should be avoided unless a fungal infection is diagnosed as they may interfere with buparlisib metabolism.

11.6 Guidelines for the treatment of buparlisib induced diarrhea

The investigator should consider/investigate potential concomitant medication, food or comorbidity driven causes of diarrhea (including infectious causes) and remedy these causes if possible (e.g. discontinuation of concomitant medication, dietary modification, treatment of comorbidity).

The patient should be monitored for signs of dehydration and instructed to take preventive measures against dehydration as soon as diarrhea occurs. Concomitant medication for the treatment of diarrhea should be considered, as per local practice and best investigator's judgment and may consist for example, as per "the recommended guidelines for the treatment of cancer treatment-induced diarrhea" (Benson 2004), of loperamide given at a standard dose (e.g. initial administration of 4mg, then 2mg every 4 hours, maximum of 16 mg/day), along with oral hydration and dietetic measures could be considered for Grade 1-2 diarrhea. More severe diarrhea should be treated appropriately according to investigator discretion, including for example IV fluids.

Dose adaptations of buparlisib in case of treatment related diarrhea should follow the guidelines presented above for other non-hematological adverse events.

11.7 Guidelines for the treatment of buparlisib induced psychiatric disorders

Psychiatric adverse events will be closely monitored and evaluated at each planned visit until recovery to Grade ≤ 1 or baseline status. The grading of psychiatric adverse events/mood alterations must be based on the clinical interpretation of severity according to the NCI- CTCAE (v 4.03) guidelines.

For patients who experience new or worsening of existing psychiatric AEs of Grade ≥ 1 , psychiatric consultation should be considered as described in Table 11.

Patient self-reported mood questionnaires (GAD-7 and PHQ-9) will be used for screening and during the study treatment phase to aid the investigator in identifying new or worsening of events. For additional information regarding safety assessments based on patient self-reported mood questionnaires, please refer to Section Patient self-rating mood questionnaires.

If question 9 in the PHQ-9 has a positive response (as indicated by selecting "1", "2", or "3"), omit treatment with buparlisib and refer the patient for psychiatric consultation for optimal management regardless of the total questionnaire score or CTCAE grading to confirm if study drug should be interrupted or permanently discontinued. In this specific case, the psychiatric advice can overrule the patient's PHQ-9 self-assessment. During the study, subjects will be monitored at regular scheduled visits (e.g., Day 15 of Cycle 1, Day 1 and Day 15 of each subsequent cycle, and at the End of Treatment visit) by the investigator/site staff through personal interaction and the two self-reported questionnaires. Additional assessments may be done according to the clinical judgment of the investigator if desired.

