10.0 EVALUATION DURING TREATMENT/INTERVENTION

10.1 General Requirements

Table 6 describes the required procedures. All procedures may increase in frequency if clinically indicated or oriented following a toxicity/adverse event.

A complete history, vital signs (including blood pressure, pulse, respiratory rate, temperature, weight and height), physical and neurological examination (to include documentation of the patients Karnofsky performance status (Appendix 6) and NANO score as well as a serum pregnancy test for women of childbearing potential will be performed on day 1 (+/- 4 days) of each cycle.

Neuro-imaging (including contrast-enhanced MRI/CT brain and total spine) and/or CSF collection (for patients with CSF disease; through Ommaya or spinal tap; including cytology) will need to be performed on all patients on day 1 cycle 3, and each additional odd numbered cycle (+/- 4 days). Imaging will include only the side of active disease (MRI brain for patients with brain disease; MRI total spine for patients with intraspinal disease; MRI brain and total spine for patients with brain and spine disease as well as leptomeningeal disease) or sides suggested by new neurologic symptoms and signs. All MRI imaging will included MR perfusion . If MRI spectroscopy is additionally performed, we will collect the additional data.

CBC with differential, platelets, sodium, potassium, calcium, AST, ALT, alkaline phosphatase, total bilirubin, fasting plasma glucose, creatinine, will need to be performed at day 1 and day 15 of each cycle and at the end of the treatment (+/- 4 days).

Amylase and lipase need to be assessed at the end of the treatment (+/- 4 days).

Chest X-ray and 12-lead ECG need to be done every other cycle starting at day 1 of cycle 3 (+/- 4 days)

Participants need to complete the PHQ-9 and GAD7 self rating mood scale (see Appendix 6).at day 1 and day 15 of cycle 1 and 2. On each consecutive cycle only on day 1 and at the

**MEMORIAL SLOAN-KETTERING CANCER CENTER
IRB PROTOCOL**

IRB#: 14-177 A(5)

end of treatment (+/- 4 days). Questionnaires can be performed over the phone on Cycle 2 Day 15 by research staff, if the participant is not able to physically attend to clinic.

Table 6: Required Activity Calendar

Tests and procedures	Screening	On trial						
		Prior to Registration	Cycle 1		Subsequent cycles		End of treatment	30-day post drug
			Day 1	Day 15	Day 1	Day 15		
Informed consent	X							
Inclusion/exclusion criteria	X							

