History, Physical and neuroexam	X	X		X		X	X	
Vital signs (blood pressure, pulse, respiration rate, temperature, height, weight) and KPS (Appendix 6)	X	X		X		X	X	
Serum pregnancy test (if applicable)	X	X		X		X		
Adverse event assessment	X			X		X	X	
Hematology group (CBC & diff)	X	X	X	X	X	X		
Chemistry group (Sodium, Potassium, Calcium, AST, ALT, Alk Phos, Total Bilirubin, Glucose, Creatinine)	X	X	X	X	X	X		
Fasting plasma glucose	X	X	X	X	X	X		
Coagulation (PT, PTT, INR)	X	X		X		X		
HbA1c	X							
8h fasting C-peptide	X							
Lipid panel	X			X*				
Amylase, lipase	X					X		
LDH	X							
Hepatitis B and C screen	X							
12-lead EKG	X			X ^s				
Chest X-ray				X ^s				
MUGA/ECHO	X							
HIV screen	X							
Bone marrow aspirate and biopsy	X							
PET brain and body	X							
PHQ-9 Patient self-rating mood scale	X		X	X	X (1)	X		
GAD7 Patient self-rating mood scale	X		X	X	X (1)	X		
NANO Score Assessment	X			X ^s		X		
Cerebrospinal fluid (CSF) Analysis including cytology	X			X(2)		X(2)		
Contrast-enhanced MRI/CT of the brain and total spine with perfusion	X			X(3)		X(3)		
Response evaluation				X (4)		X		
Computed tomography of chest, abdomen, pelvis	X							
Ophthalmologic evaluation including slit lamp exam	X							
PK BKM120 CSF			X(5)					
PK BKM120 Blood			X(6)					
Blood collection for genomic DNA			X					
Collection of archival FFPE tumor samples	X						X(7)	

- (1): PHQ-9 and GAD7 will be collected on day 15 of cycle 1 and day 1 and day 15 during cycle 2; then only on day 1 on subsequent cycles
 (2): Collection on day1 of all odd cycles starting on cycle 3; for patients with CSF disease only; response to treatment will be measured in CSF (+/- 4 days)
 (3): Imaging on day 1 of all odd cycles starting with cycle 3; MRI brain for patients with brain disease, MRI total spine for patients with intraspinal disease; MRI brain and total spine for patients with brain and spine disease as well as leptomeningeal disease (+/- 4 days)
 (4): Response will be evaluated on day 1 of all odd cycles starting with cycle 3
 (5): Patients with Ommaya reservoir: CSF collection at 1h, 2h, 4h after drug administration; no Ommaya: CSF collection through

lumbar puncture 2h after drug administration (+/- 30 min)

(6): Patients with Ommaya reservoir: Blood collect parallel to CSF collection at 1h, 2h, 4h after drug administration; no Ommaya: blood collection parallel to CSF collection through lumbar puncture 2h after drug administration (+/- 30 min)

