10.4 Patient self-rating mood questionnaires

The Patient Health Questionnaire-9 (PHQ-9) and Generalized Anxiety Disorder-7 (GAD-7) will be collected to screen patients for the study and to aid in the identification and severity assessment of potential mood alterations. The PHQ-9 and GAD-7 are validated (Kroenke 2001, Spitzer 2006, Spitzer 1999), patient self-administered questionnaires developed for use in clinical practices.

The PHQ-9 consists of 9 questions that assess anhedonia, depressed mood, sleep, energy, appetite, guilt and worthlessness, concentration, feeling slowed down or restlessness, and suicidal thoughts. For each of these questions, patients are asked to rate how much over the past 2 weeks they have been bothered by the symptom. Scoring of the PHQ-9 is based on a Likert-type scale from 0 to 3 (0

MEMORIAL SLOAN-KETTERING CANCER CENTER
IRB PROTOCOL

IRB#: 14-177 A(5)

indicates not at all; 1, several days; 2, more than half the days; 3, nearly every day). The sum of all nine questions is used to determine a total PHQ-9 score ranging from 0 to 27.

The GAD-7 is a one-dimensional questionnaire consisting of 7 questions. Similarly to the PHQ-9, in the GAD-7, patients are asked to indicate how often, over the past 2 weeks, they have been bothered by each of the seven core symptoms of generalized anxiety disorder as referenced in the DSM IV. Response options are “not at all” “several days” “more than half the days” and “nearly every day” scored as 0, 1, 2, and 3, respectively. The sum of all seven questions calculates the total GAD-7 score. Therefore, GAD-7 scores range from 0 to 21. The patient must complete two different mood questionnaires, (PHQ-9 and GAD-7) at Screening, at collection on day-1 or within the screening, then on day 15 of cycle 1 and day 1 and 15 of cycle 2 and on day 1 of subsequent cycles, as well as at end of treatment. Additional assessments may be done according to the clinical judgment of the investigator. All questionnaires should be administered in the patient’s local language at the beginning of the study visit prior to any interaction with the study investigator including any tests, treatments or receipt of results from any tests to avoid biasing the patient’s perspective. This is to avoid potentially biasing patients or their responses to study questionnaires.

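### From cycle 3 the PHQ-9 and GAD-7 are scheduled every 28 days, while section 11.7 describes them every 14; this is a gap in questionnaire spacing, not in all mood surveillance

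*Combined protocol and SAP*

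**What the plan says.** Section 11.7 covers psychiatric toxicity. It states that "subjects will be monitored at regular scheduled visits (e.g., Day 15 of Cycle 1, Day 1 and Day 15 of each subsequent cycle", and at end of treatment, "by the investigator/site staff through personal interaction and the two self-reported questionnaires". The visit list is introduced as an example.

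Three other places set the questionnaire schedule, and they agree with each other from cycle 3:

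- Section 10.1: "On each consecutive cycle only on day 1", plus end of treatment.
- Section 10.4: "then on day 15 of cycle 1 and day 1 and 15 of cycle 2 and on day 1 of subsequent cycles".
- Table 6, footnote 1: "then only on day 1 on subsequent cycles".

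In Table 6 the row "Adverse event assessment" is marked at screening, day 1 of subsequent cycles, end of treatment and 30 days after the last dose. It is blank in both day 15 columns, as is the history and examination row. Blood tests are scheduled on day 15 of every cycle (10.1).

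Section 10.4 gives the recall period of the PHQ-9: patients rate "how much over the past 2 weeks they have been bothered by the symptom". The GAD-7 has the same two-week period.

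**The concern.** The plan treats mood toxicity as a major hazard. Section 6.2 excludes patients with a PHQ-9 score of 12 or more, a GAD-7 score of 15 or more, or any positive answer to item 9. On treatment, a positive item 9 requires that the drug be held and the patient referred to psychiatry (10.4, 11.7, Table 11). Table 11 also requires holds for Grade 2 and Grade 3 mood events. These rules act only once the problem has been found, and item 9 is read only when the form is given.

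Sites therefore have two different descriptions of how often that screen happens from cycle 3. Under the operative schedule it happens half as often as 11.7 describes, and suicidal thoughts that arise and settle between forms need not reach the item 9 rule.

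**Working it through.** The plan states no figure to reproduce, so the check compares the schedules and counts visits.

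**Questionnaire days, by source**

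| Source | Cycle 1 | Cycle 2 | Cycle 3 onward |
|---|---|---|---|
| 11.7 | D15 | D1, D15 | D1, D15 |
| 10.1 | D1, D15 | D1, D15 | D1 |
| 10.4 | D1 or within screening; D15 | D1, D15 | D1 |
| Table 6, footnote 1 | D15 | D1, D15 | D1 |

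**Count over cycles 1 to 6 (24 weeks), without screening and end of treatment.** Table 6 and 10.4: 3 forms in cycles 1 and 2 (leaving out cycle 1 day 1) + 4 day 1 forms in cycles 3 to 6 = 7. Section 11.7: 1 + (5 cycles × 2) = 11. The 4 missing are day 15 of cycles 3, 4, 5 and 6.

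**Interval from cycle 3** (28-day cycle, 9.1). 28 days against 14. If the ±4 day window in 10.1 applies at each end, the longest intervals are 28 + 8 = 36 and 14 + 8 = 22 days.

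**Mean wait to the next form**, assuming onset uniform over the interval: 28/2 = 14 days against 14/2 = 7 days.

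**Recall.** A two-week look-back covers 14 of 28 days; the other 14 (50%) lie outside any form. An event that persists to day 1 is still captured, and the day 1 history is not limited to two weeks.

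**Scale.** Table 10 gives drug-related altered mood in 17/81 (21%), grade 3/4 in 4/81 (4.9%), without timing. Scaled to 21 patients: 17/81 × 21 = 4.4 and 4/81 × 21 = 1.04. If 10% to 50% of these begin after cycle 2 (an assumption; the documents give no share), that is 0.44 to 2.2 patients, of whom 0.10 to 0.52 grade 3/4. These would be events beginning in the period, not events missed.

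**Cost of adding day 15 forms.** Day 15 of cycle n is study day 28(n − 1) + 15, so cycles 3 to 6 give days 71, 99, 127 and 155.

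- Upper bound to week 24: 4 × 21 = 84. To week 48 (cycles 3 to 12): 10 × 21 = 210.
- With attrition, assuming exponential PFS and treatment until progression: 21 × Σ p^(d/168), where p is PFS24w and d the study day. At p = 0.34 (the section 14.0 benchmark) this is 41.5 to week 24 and 67.5 to week 48. At p = 12/21 it is 58.0 and 112.9.

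**Table 6 columns.** The hematology row fills both day 15 columns, while the adverse event and examination rows leave both blank. Section 10.1 separately places history and examination on day 1 of each cycle, which agrees.

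**The case against.** A reader might infer that from cycle 3 day 1 is the only scheduled point at which a new mood event can be found. The documents do not support that. Section 11.7 pairs the questionnaires with personal interaction by site staff. The three schedule statements restrict only the questionnaires, and nothing cancels the interaction. Patients have day 15 blood tests in every cycle. Section 9.1 collects all adverse events from the first dose and requires at least weekly checks once an event leads to a delay or reduction. Section 11.7 adds: "Psychiatric adverse events will be closely monitored and evaluated at each planned visit until recovery to Grade" 1 or baseline. Section 11.3 has patients routinely asked about adverse events, though with no date. Sections 10.4 and 11.7 both allow additional assessments on clinical judgment.

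Nor do the blank day 15 cells leave cycles 1 and 2 unwatched. Section 10.4 requires the investigator to review every completed form for possible adverse events, and forms are given on day 15 of both cycles.

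It can also be said that the working schedule is clear. The 11.7 list is only an example and refers the reader to the questionnaire section, the taper is stated three times, and the telephone option in 10.1 is written for cycle 2 day 15 alone. That suggests a deliberate choice, and nothing in the documents shows that monthly forms are too sparse.

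Most of this stands, and it limits the harm. It does not remove the mismatch: 11.7 names day 15 of later cycles as a visit at which both forms are used, and the schedule excludes it. None of the remaining safeguards puts a dated item 9 screen at mid-cycle.

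**Conclusion.** The inconsistency is real and confined to questionnaire spacing. From cycle 3 the scheduled PHQ-9 and GAD-7, and with them the item 9 screen, come every 28 days rather than the 14 in 11.7, and half of each cycle falls outside the forms' recall. Day 15 of those cycles has a blood draw but no form, adverse event entry or examination marked in Table 6.

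How many patients this touches is unknown, because the documents give no timing of mood events and no rate of suicidal ideation. The 0.4 to 2.2 patients shown above rest entirely on the assumed late-onset share, and probably few of those would be missed. The PFS24w analysis and the sample size are unaffected. The change is worth making because the screen triggers a mandatory hold and extending it is cheap. Whether the taper was intended cannot be settled from the documents.

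**What to change.** Give PHQ-9 and GAD-7 on day 1 and day 15 of every cycle from cycle 2:

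- Table 6, footnote 1: replace "then only on day 1 on subsequent cycles" with *then on day 1 and day 15 of subsequent cycles*.
- Section 10.1: replace "On each consecutive cycle only on day 1" with *On each consecutive cycle on day 1 and day 15*.
- Section 10.4: make the same change to the schedule sentence.
- Table 6: mark the adverse event row in the day 15 column for subsequent cycles. Cycle 1 day 15 needs no extra check beyond the form review in 10.4.
- Administer the forms at the existing day 15 blood draw, or extend the telephone option from cycle 2 day 15 to every later day 15. Because research staff may make the call, require same-day notice to the investigator of a positive item 9.

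Section 11.7 then stands as written.

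The cost is amendment wording plus one short contact, with the form review and source documentation that 10.4 requires, per patient per cycle from cycle 3. Contacts continue past week 24 for patients still on treatment. The adverse event mark also covers cycle 2 day 15, at most 21 brief entries (1 × 21) at a contact that already carries the forms.

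If the sponsor confirms that the taper is deliberate, align 11.7 with 10.4 and state the reason. That costs nothing, but it is a consistency edit only and does not shorten the interval.
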